7.3.2 Subject Preparation for PCDT Procedures

- Steroid Pre-Medication: In subjects with contrast allergies, steroid pre-medication should be started 12-24 hours before PCDT, per the Center's standard practice. A histamine receptor antagonist (e.g., diphenhydramine) should also be given before contrast is administered. Both the steroids and the histamine receptor antagonist should be continued throughout the period when contrast may be administered (i.e., for multisession procedures).
- 2. Reversal of Elevated INR: In subjects with an INR > 1.6, Vitamin K should be given orally, subcutaneously, or by intravenous infusion to bring the INR to 1.6 or below before PCDT.
- 3. Pre-procedure Hydration: Subjects should receive pre-procedure hydration as dictated by their renal function, overall clinical status, and the physician's standard practice.
- 4. IVC Filter Placement: As outlined in Section 6.2.5, in selected subjects a retrievable IVC filter may be placed at the endovascular physician's discretion. The filter may be placed per the institution's standard practice at any time before PCDT, with these caveats:
 - a) An ultrasound-guided venous access should be used. If the filter is placed within 48 hours before PCDT, a venous sheath or catheter should be left in place until at least 1 hour after the last administration of rt-PA (to avoid puncture site bleeding).
 - b) An IVC venogram must be obtained to ensure accurate filter deployment.
 - c) Non-ionic iodinated contrast should be used to minimize risk to the kidneys.
 - d) A retrievable Tulip filter (Cook Inc., Bloomington, IN) should be used.
 - e) The filter should be deployed in the infrarenal IVC, if possible.

7.3.3 Phase 1 - Procedure Initiation

PCDT procedures should be initiated using the following accepted endovascular practices (63):

- 1. The endovascular physician should review the baseline imaging studies, examine the affected lower extremity with ultrasound, and select a primary venous access site.
- 2. An intravenous line should be placed and conscious sedation initiated with continuous monitoring of heart rate, oxygen saturation, blood pressure, and cardiac rhythm.
- 3. Sterile technique must be used during all endovascular procedures.
- 4. Local anesthesia should be injected into the skin over the venous access site(s).
- 5. Catheter access into the deep venous system should then be obtained this must be done using ultrasound-guided puncture (to prevent inadvertent arterial punctures) of the selected lower extremity vein (e.g., the ipsilateral popliteal vein) or the right internal jugular vein. The physician may access additional veins under ultrasound guidance at his/her discretion. The physician is strongly encouraged to choose a venous access strategy that will enable direct treatment of any popliteal and/or below-knee thrombus that is needed to ensure adequate inflow into the proximal veins. The use of the contralateral common femoral vein for access is, however, strongly discouraged. The use of the femoral vein in the mid-thigh is prohibited.
- 6. Real-time fluoroscopic monitoring of catheter/guidewire manipulations should be used.
- 7. A catheter should be advanced into the venous system and a baseline venogram of the proximal veins (popliteal vein through infrarenal IVC) should be obtained with digital imaging and serial hand-injections of 5-10 ml non-ionic iodinated contrast, diluted as needed with normal saline, through the catheter at 10-20 cm intervals. Automated power injection is not permitted. **Note:** As the thrombus extent on the baseline venogram is relevant to the study data analysis, care should be taken to obtain complete imaging of the thrombus extent, even if this requires contrast injections from within non-flowing iliac or femoral venous segments.
- The endovascular physician should examine the venogram. Based upon the presence or absence of good popliteal vein inflow and IVC thrombus, the physician should follow the guidelines provided in Section 6.2.4 to determine which PCDT technique must be used.
- The catheter should be exchanged for a vascular sheath to maintain deep venous access and to enable repeat venograms to be performed to monitor thrombolytic progress.

7.3.4 Phase 2 - Performance of Initial PCDT

- Initial PCDT: The steps in Appendix 4 (for Trellis PCDT), Appendix 5 (for AngioJet PCDT), or Appendix 6 (for Infusion-First PCDT) should then be followed to deliver rt-PA into the thrombus. After completion of those steps, proceed to the steps in Section 7.3.5 below.
- 2. Treatment Cessation or Reduction of rt-PA Dose: During PCDT, the physician may reduce the rt-PA dose or stop it entirely at his/her discretion if there are safety concerns. If serious bleeding occurs at the venous access site (uncontrolled by sheath upsizing or compression), rt-PA administration should be stopped. If sheath upsizing and/or compression are effective in stopping the bleeding, rt-PA may be re-started at a lower dose. If serious bleeding occurs in a distant location, or if a severe or life-threatening reaction occurs, administration of rt-PA should be permanently stopped. If serious bleeding occurs, infusion of UFH should also be stopped and, at physician discretion, protamine and/or cryoprecipitate may be given.

7.3.5 Phase 3 - Clean-Up of Residual Thrombus

- A repeat venogram should be obtained through the sheath or a catheter. If nearcomplete (> 90%) lysis and good anterograde flow are observed (by visual estimation) with no venous stenosis or obstruction, treatment may be stopped at any time thereafter at the physician's discretion – in this situation, proceed to Section 7.3.7. If near-complete (> 90%) lysis is observed but there is significant venous stenosis or obstruction, proceed to Section 7.3.6.
- 2. If residual thrombus is present, the physician may use the following adjunctive measures. To minimize the risk of causing PE, these methods should not be used prior to completion of initial PCDT (Techniques A and B) or at least 4 hours of rt-PA infusion (Technique C). The decision as to which method(s) are used, and the sequence, may be determined by the physician to allow maximum flexibility to tailor therapy to individual patient circumstances.
 - a) Balloon Maceration of the thrombus may be performed as follows: Advance a standard angioplasty balloon catheter (6-10 mm for the femoral vein, 10-12 mm for the common femoral vein or iliac vein) over the guidewire into the thrombus. Inflate the balloon within the thrombus under fluoroscopic guidance using the physician's usual technique. Deflate the balloon. Repeat these steps as needed with the balloon positioned in different parts of the thrombus. Remove the

angioplasty balloon catheter over the guidewire.

- b) Aspiration thrombectomy may be performed as follows: Advance a standard 7-8 French catheter over the guidewire to the cephalad aspect of the thrombus. Attach a large (30- 60 ml) syringe to the catheter. Vigorously aspirate with the syringe during withdrawal of the catheter through the thrombus – this may be done with the guidewire in place or with the guidewire removed. Repeat these steps as needed, then remove the catheter.
- c) Rheolytic thrombectomy may be performed using the AngioJet in aspiration mode, as described in **Appendix 5**, Steps 5-9. The precautions cited in **Appendix 5** regarding guidewire retraction, infusate volume, and device activation time should be followed.
- d) Additional rt-PA boluses (up to 5 mg rt-PA per session) may be given at the physician's discretion, but the total rt-PA dose may not exceed 35mg for all sessions combined. The additional rt-PA may be delivered in the following ways:
 (1) via injection through the vascular sheath or a multisidehole catheter; (2) in Technique A patients only, via the Trellis as described in Appendix 4, Steps 4-8; or (3) in Technique B patients only, via the Angiojet (PowerPulse or Rapid Lysis method) as described in Appendix 5, Step 4.
- 3. Perform a repeat venogram. If significant residual obstructing thrombus is present, position a multisidehole infusion catheter within the thrombus and perform Infusion CDT (rt-PA at 0.01 mg/kg/hr, maximum dose 1.0 mg/hr) as outlined in **Appendix 6**. (For Technique C subjects, this will simply represent a continuation of the initial rt-PA infusion.) The rt-PA infusion should continue until near-complete (> 90%) thrombolysis is observed, clinically-overt bleeding becomes evident, or until a maximum of 24 hours (for Technique A or Technique B) or 30 hours total (for Technique C) of rt-PA infusion has occurred.
- 4. The steps in Section 7.3.5 may be repeated as needed, but the above limits on rt-PA dose, infusion duration, device activation time, and AngioJet infusate volume must be followed.

7.3.6 Phase 4 - Treatment of Obstructive Lesions

1. At physician discretion, balloon angioplasty and/or stent placement may be performed to correct areas of venous stenosis or obstruction, pursuant to the guidelines in

Section 6.2.5.

2. Venography should be repeated after balloon angioplasty and/or stent placement.

7.3.7 Phase 5 - Completion of PCDT Procedures

- 1. The physician should perform a venogram that documents the status of the proximal deep veins (popliteal vein through IVC). **Note:** As the thrombus extent on the final venogram will be analyzed as a study outcome, care should be taken to obtain complete imaging of the extent of thrombus, even if this requires contrast injection from within non-flowing segments.
- When therapy is completed, the sheath may be removed at the physician's discretion, but no less than 1 hour after the last rt-PA dose or UFH bolus dose was given. Hemostasis should be achieved via manual compression. The subject should remain at bedrest with the treated leg immobile for 6 hours, after which he/she may ambulate as tolerated.
- Therapeutic-level anticoagulation should be resumed within 2 hours after hemostasis is obtained. If UFH is used, a bolus dose should not be given. Subjects receiving LMWH should continue their previous regimen of scheduled injections.
- 4. Warfarin should be initiated on the same day as sheath removal. Warfarin intensity, duration of therapy, INR monitoring, overlap with heparin therapy, and hospital discharge should be managed in the same way as in the Control Arm (Section 7.2). However, PCDT subjects may not be discharged from the hospital until at least 12 hours after sheath removal.
- 5. For subjects in whom a retrievable IVC filter was placed prior to PCDT, careful attention should be paid to ensuring timely removal of the filter. The filter may be removed at any time interval after PCDT that is consistent with safe clinical practice. In general, removal of the filter as soon as possible (e.g. within 3 days) after completion of PCDT is encouraged. If this cannot occur, the subject should be assessed at the 10-day follow-up visit for the ability to have the filter removed, and similarly re-assessed at least every 3 weeks thereafter until the filter has been removed or 3 months have elapsed since the date of its original insertion. There is no need to stop anticoagulation for filter retrieval unless it is supra-therapeutic. The retrieval may be performed per the physician's standard practice, but an ultrasound-guided jugular vein approach should be used to avoid inadvertent arterial punctures and trauma to the leg veins. Two conditions should be met before filter retrieval: (a) the subject must be therapeutically anticoagulated; and

(b) on venography or contrast-enhanced CT scan, the subject must not have significant thrombus within the filter (\geq 25% of the filter's volume) or within the IVC below the filter (94,95). If either condition is not met, the filter should be left in place and removed when these criteria are satisfied. The filter should only be left in place permanently in the following situations: (a) the patient has a strong indication for long-term caval interruption, per the criteria outlined in Section 6.1.4; (b) the filter proves to be difficult to remove without extensive catheter manipulation that would risk injury to the caval wall; or (c) the filter could not be removed within 3 months after the date of its original insertion.

8 EFFICACY OUTCOMES

8.1 Primary Efficacy Outcome

Post-Thrombotic Syndrome (PTS) defined by the presence of a total score of 5 or greater on the Villalta PTS Scale in the leg with the index DVT, or an ulcer in that leg, that occurs at any time between the 6-month post-randomization follow-up visit and the 24-month visit (inclusive).

8.2 Secondary Efficacy Outcomes

- PTS occurrence at 6, 12 and 18 months, assessed using Villalta PTS Scale (as above).
- Major non-PTS treatment failure during 24 months (see Section 15.3.7 for definition)
- Composite of PTS occurrence + major non-PTS treatment failure during 24 months
- PTS severity at 6, 12, 18 and 24 months, assessed using:
 - a) Villalta PTS Scale
 - b) Venous Clinical Severity Score (VCSS)
 - c) Clinical Class in the Clinical-Etiologic-Anatomic-Pathophysiologic (CEAP) System.
- Quality of Life (QOL) at 1, 6, 12, 18 and 24 months, assessed using:
 - a) SF-36v2 measure (general QOL)
 - b) VEINES-QOL/Sym measure (venous disease-specific QOL).
- Resolution of leg pain at 10 days and 1 month, assessed using Likert scale scores.
- Resolution of leg swelling at 10 days and 1 month, assessed using standardized measurement of calf circumferences.
- Degree of clot lysis with PCDT, assessed venographically (Experimental Arm only).
- Prevalence of valvular reflux and residual thrombus at 1 year (Duplex ultrasound).
- Cost-effectiveness, measured in dollars per quality-adjusted life-year (QALY).

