4 SUBJECT SELECTION

4.1 Subject Identification and Index Leg Designation

At the Clinical Centers, subjects will be identified by Vascular Ultrasound Laboratory personnel who diagnose DVT, by pharmacy personnel who dispense anticoagulant drugs, by Emergency Department physicians and hospital physicians who treat DVT patients, and by the ATTRACT investigator physicians. Subjects may also be referred from regional facilities.

For patients who present with bilateral DVT, the investigator must designate which lower extremity will be considered the "index leg" to be used in the study outcome analyses. In general, the index leg should be the leg that would be most likely to prompt the use of PCDT in clinical practice. Designation of the index leg must be documented prior to randomization.

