4.5 Baseline Evaluation

After eligibility is established and informed consent is obtained, but before randomization, subjects should undergo the following baseline assessments (see Section 8 for details):

- Self-completion of QOL questionnaires (SF-36v2, VEINES);
- Self-rating of baseline leg pain (7-point Likert scale) (both legs);
- Calf circumference measurement (both legs);
- Administration of Villalta's PTS Scale (both legs); and
- Venous Duplex ultrasound of the index leg. A previous ultrasound may be used if it was
 performed within 5 days prior to randomization, provided that its scope was adequate
 (i.e. compression of the proximal veins of the leg was clearly documented, enabling entry
 of this information on the Compression Ultrasound Case Report Form).
- Examination of the contralateral lower extremity is encouraged but optional; if performed, the findings should also be entered on the Compression Ultrasound Case Report Form.

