8.11 Resolution of Leg Pain and Swelling

To determine if PCDT leads to faster DVT symptom resolution, the severity of pain in each leg will be assessed on a 7-point Likert scale at baseline and 10-day and 1-month follow-up. The subject will be asked to "Please rate the overall intensity of "pain" or "discomfort" that you have felt in your leg during the past 24 hours by checking one response on the following scale" (1 = No pain, 2 = Very mild pain, 3 = Mild pain, 4 = Moderate pain, 5 = Severe pain, 6 = Very severe pain, 7 = Extremely severe pain). Likert scales are widely validated for pain severity assessment (114,115). The Likert scale and accompanying instructions will be available in the originally validated English version and in a certified Spanish translation. Calf circumference 10cm below the tibial tuberosity will also be measured at baseline and 10-day and 1-month follow-up. At these visits, venous symptoms and signs will also be assessed using the Villalta PTS Scale. The clinician performing these assessments must be blinded to subject treatment allocation.

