11.1 Scheduled Visit 1 – Follow-Up Assessment at 10 Days

At 10 days ± 3 days after randomization, subjects:

51

- rate their leg pain (7-point Likert scale) (both legs)
- have their leg circumference measured (both legs)
- undergo assessment using the Villalta PTS Scale (both legs)
- are provided sized-to-fit elastic compression stockings (ECS)
- have their platelet count obtained to assess for heparin-induced thrombocytopenia (HIT)
- have adverse events, thrombotic and bleeding events, hospitalizations, physician visits, anticoagulant regimen, and their cost diary reviewed and recorded
- are re-assessed for removal of a retrievable IVC filter (if one is present)

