15 STATISTICAL METHODS

15.1 Sample Size Calculation

The goal of the ATTRACT Trial is to determine if adjunctive PCDT (Experimental Arm), compared with optimal standard DVT therapy alone (Control Arm), reduces the 2-year occurrence of PTS in subjects with symptomatic proximal DVT. Based on previous studies (2-5), 30% of subjects in the Control Arm are expected to have PTS within 24 months of DVT diagnosis. Based on the expected success of PCDT at restoring venous patency and reductions of PTS that were achieved with thrombolytic therapy in earlier studies (33,34,42,51,52,139), we hypothesize that PCDT will reduce the risk of PTS by at least 33%. Accepting a 5% chance of incorrectly concluding that there is a difference in the proportion of subjects with PTS at 24 months with PCDT (α error=0.05; two-sided), and the requirement that the study has an 80% chance (β error=0.2) of detecting a true difference if PCDT truly reduces PTS by 33%, 311 subjects in each group must be studied (based on the Fisher's exact test).

In recently completed studies of long-term treatment for unprovoked VTE coordinated by the DCC, loss to follow-up or death occurred in 2.5% during 2 years follow-up (140), and in 3.4% during mean follow-up of 2.4 years (141). We therefore expect no more than 5% of randomized subjects to be lost to follow-up at 24 months. However, to ensure that statistical power will not be compromised, we will assume that as many as 10% of randomized subjects (double the maximum expected) will not complete the 24-month assessment. Therefore, we plan to randomize 346 subjects to each group, yielding a total study sample size of **692 subjects**.

For the secondary analyses, 692 subjects will provide approximately 88% power to detect an effect size of 0.25 with continuous outcomes. QOL changes from baseline: This translates into the ability to detect a difference of 1.25 in the VEINES-QOL change scores, and 2.5 in the SF-36v2 PCS and MCS change scores (change of 4 points is clinically important for all 3 scales).

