15.3 Secondary Analyses

Secondary analyses will be performed using both analysis sets. To account for multiple testing, a two-sided p-value of 0.01 or less will be considered statistically significant for all tests (144).

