15.3.11 Resolution of Acute Symptoms

Mean absolute change in severity of leg pain, measured using a 7-point Likert scale, from baseline to 10 days and 1 month after randomization will be compared between the two arms using an analysis of co-variance. Leg circumference (measured and percentage change in leg circumference compared to pretreatment values), at 10 days and 1 month will be compared between the two arms using the Student's t-test. In the PCDT group, the mean change scores in leg pain and leg circumference will be correlated with degree of thrombus removal as assessed by mean change in Marder scores between pre-PCDT and post-PCDT venograms.

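### Leg swelling is to be compared by t-tests on measured and percentage-change circumference, with no use of the other calf that is measured at the same visits; this costs precision and interpretability, not validity

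*Protocol*

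**What the plan says.** Section 8.2 names the outcome: "Resolution of leg swelling at 10 days and 1 month, assessed using standardized measurement of calf circumferences". Section 8.11 gives the site: "Calf circumference 10cm below the tibial tuberosity will also be measured at baseline and 10-day and 1-month follow-up".

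Both legs are measured. Section 4.5 lists at baseline "Calf circumference measurement (both legs"), and section 11.1 has subjects at 10 days "have their leg circumference measured (both legs"). Section 11.2 repeats this for 1 month.

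The analysis is in section 15.3.11: "Leg circumference (measured and percentage change in leg circumference compared to pretreatment values), at 10 days and 1 month will be compared" between the arms by Student's t-test. The sentence names no leg and includes no between-leg difference. In the same section, leg pain is compared by analysis of covariance.

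For patients with bilateral DVT, section 4.1 has the investigator designate "which lower extremity will be considered the 'index leg' to be used in the study outcome analyses". For secondary analyses, section 15.3 states that "a two-sided p-value of 0.01 or less will be considered statistically significant for all tests".

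**The concern.** A calf circumference is the subject's normal calf plus whatever swelling is present. Normal calves differ between people by several centimetres, probably more than swelling does, so a t-test on the measured value puts most of its variance into body size.

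Percentage change makes each subject their own control, but the reference is the leg at presentation, already swollen. It says how far the leg shrank, not whether it reached normal. The other calf is the obvious reference for normal size and is already measured, yet the stated analysis leaves it out.

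At stake is how sharply and how clearly one secondary outcome, tested at 0.01, can show an early benefit on swelling.

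**Working it through.** **The plan's own figure.** Section 15.1 gives no SD, effect or power for circumference. The only figure that covers it is general: "692 subjects will provide approximately 88% power to detect an effect size of 0.25 with continuous outcomes". With 311 evaluable per arm (section 15.1) and two-sided alpha 0.05, power = Φ(0.25 × √(311/2) − 1.960) = Φ(3.117 − 1.960) = 0.876, so the 88% reproduces. At alpha 0.01, Φ(3.117 − 2.576) = 0.706. An effect size of 0.25 means 0.25 SD, so what it means in centimetres depends on which variable is analysed.

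**What percentage change can show.** Take an unswollen calf of 38 cm:

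- 40 to 38 cm: −2/40 = −5.0%, residual swelling 0 cm
- 42 to 39.9 cm: −2.1/42 = −5.0%, residual 1.9 cm
- 43 to 40.85 cm: −2.15/43 = −5.0%, residual 2.85 cm

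The same result covers full and partial resolution.

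**Precision, on assumptions.** Every SD here is assumed: calf size 3-4 cm; swelling 1.5-2.0 cm at baseline and 1.0-1.5 cm at follow-up, correlation 0.4; natural left-right difference 0.5-1.2 cm; measurement error 0.3-0.5 cm.

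Model: index baseline I0 = size + swelling0 + error; index follow-up I1 = size + swelling1 + error; other leg C = size + asymmetry + error.

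Scenario 1 (size 4, swelling 1.8 and 1.2, asymmetry 0.5, error 0.5):

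- Var(I0) = 16 + 3.24 + 0.25 = 19.49
- Var(I1) = 16 + 1.44 + 0.25 = 17.69
- Cov(I0, I1) = 16 + 0.4 × 1.8 × 1.2 = 16.864
- Var(C0) = 16 + 0.25 + 0.25 = 16.50; Cov(I, C) = 16

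Residual variances:

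- Measured value: 17.69 (SD 4.21)
- Change: 19.49 + 17.69 − 2 × 16.864 = 3.452 (SD 1.86)
- ANCOVA, index baseline only: 17.69 − 16.864²/19.49 = 3.098 (SD 1.76)
- ANCOVA, both baselines: coefficients 0.3393 (index) and 0.6406 (other leg); 17.69 − (0.3393 × 16.864 + 0.6406 × 16) = 1.717 (SD 1.31)
- ANCOVA on the leg difference: variances 2.19 and 3.99, covariance 0.864 + 0.25 = 1.114; 2.19 − 1.114²/3.99 = 1.879 (SD 1.37)

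In scenario 1, an effect size of 0.25 is 0.25 × 4.21 = 1.05 cm on the measured value and 0.25 × 1.31 = 0.33 cm with both baselines.

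Scenario 2 uses size 3, swelling 1.5 and 1.0, asymmetry 1.2 and error 0.5. Scenario 3 adds independent visit-to-visit variation of SD 0.5 cm in the other leg.

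| Residual variance | 1 | 2 | 3 |
|---|---|---|---|
| Measured | 17.69 | 10.25 | 10.25 |
| Change | 3.45 | 2.55 | 2.55 |
| ANCOVA, index only | 3.10 | 2.24 | 2.24 |
| ANCOVA, both legs | 1.72 | 1.63 | 1.67 |
| ANCOVA, leg difference | 1.88 | 1.95 | 2.25 |

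Cut from two-leg ANCOVA against index-only ANCOVA: 45%, 27%, 25%. Against the measured value: 90%, 84%, 84%. Cut from the leg difference against index-only ANCOVA: 39%, 13%, none.

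Pairing the extremes of the assumed ranges, with and without the added variation of scenario 3, widens the first two to 13-63% and 76-94%. Two-leg ANCOVA does not fall behind index-only ANCOVA in any of these, because adding a baseline covariate cannot raise the population residual variance.

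**The case against.** The strongest reply is that nothing here is wrong, only less efficient than it could be. Several parts of that stand.

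- A reader might infer that the protocol restricts the outcome to one leg. It does not say so: section 8.2 uses the plural, 15.3.11 names no leg, and 4.1 fixes the index leg for bilateral DVT. The one-leg reading is natural but inferred.
- A reader might infer that the whole outcome is confounded with body size. That fits the measured value only. In a separate simulation on assumed values (true difference 0.5 cm, 311 per arm, alpha 0.01), percentage change correlated only 0.03-0.09 with calf size and kept 68-87% power, against 0.82-0.98 and 13-61% for the measured value. A real early effect would not necessarily be hidden.
- A reader might infer bias, from body size or because section 8.9 asks for afternoon examination at follow-up while 4.5 sets no time at baseline. Both act equally on the two arms.
- The adjusted analysis in section 15.4.1 includes body-mass index and gender and would absorb some size variance. Its list has neither baseline circumference nor the other leg.
- The Villalta scale, given at the same visits, also rates edema, so circumference is not the only evidence on swelling.
- A between-leg difference does not by itself establish resolution: with natural asymmetry of 0.5-1.2 cm SD, a 1 cm difference may be normal. Scenario 3 shows that its precision gain can vanish.

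The argument that this belongs in the SAP does not stand. Section 15.3.11 itself chooses the two variables and the test.

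**Conclusion.** The point holds as a weak choice of stated method. The plan collects a natural reference for calf size and does not use it, compares circumference by t-test where leg pain in the same section gets a covariance analysis, and labels as resolution what is analysed as size or shrinkage. The cost is precision and interpretability.

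On the assumed SDs, two-leg ANCOVA saves about 20-45% of residual variance against index-leg ANCOVA and about 80-90% against the measured value, with wider limits at the extremes. The between-leg difference alone gains from nothing to about 40% against index-leg ANCOVA. That two-leg adjustment does no harm to precision is general; the size of the gain rests entirely on the assumptions. The documents do not support a claim of bias, or that the trial cannot compare reduction in swelling. Low priority.

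**What to change.** In section 15.3.11, replace the t-tests on circumference with ANCOVA of index-leg circumference at 10 days and at 1 month, adjusting for baseline circumference of both the index and the non-index leg.

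Report the index-minus-non-index difference at each visit, with ANCOVA on the baseline difference, as a supporting measure of residual swelling. Add a sensitivity analysis excluding subjects with known bilateral DVT.

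In sections 8.2 and 8.11, describe the outcome as reduction in leg swelling unless a criterion for resolution is set.

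The cost is wording and slightly more analysis; all measurements are already scheduled. The limit is that the non-index leg is an imperfect reference where it also has DVT. Exclusion 4 in section 4.3 removes only some such patients, and section 4.5 makes the baseline examination of that leg optional, so the sensitivity analysis covers known cases only.
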